According to Mitchell et al “There are two main disadvantages to CBT-I. First, during the first few weeks of treatment there is often an acute reduction in total sleep time that can lead to the side effect of increased daytime sleepiness which, for some, is enough to lead them to drop out of treatment. Second, improvements from CBT-I are typically not seen until 3-4 weeks into treatment” (p. 3 of 18). Also noteworthy is the emotional response of patients upon learning their sleep will be restricted, commonly with a markedly later bedtime during the implementation of sleep restriction. Although apparently no research to date has assessed patient satisfaction and/or distress during treatment implementation, this may be a factor related to dropout rate with CBT-I. Among ten randomized controlled trials of CBT-I for primary insomnia reporting dropout rate and involving sleep restriction, dropout rates ranged from 0% to 33%. Specifically, 4 studies reported 0% dropout; 1 study reported 7% dropout; 2 studies reported 8% dropout; and dropout rates of 11%, 18% and 33% were each reported in one study (Table 1, Okajima, Komada & Inoue, 2011). In addition, while 36% remission of insomnia disorder is better than 16.9% (comparison group), this means 64% of those completing CBT-I continued to meet diagnostic criteria for Insomnia Disorder (Wu, Appleman, Salazar and Ong, 2015). With all due respect for the major contribution of CBT-I in assisting those with insomnia, there is room for improvement as evidenced by 64% still having Insomnia Disorder upon completion of treatment.

Another potential limitation of CBT-I relates to the mechanism of change and may lead to a means to improve upon the efficacy of behavioral treatment(s) for insomnia. “Research by [name]. and colleagues has established that insomniacs have faster brain wave patterns in bed than good sleepers which is consonant with heightened mental activity.” (Jacobs, 2000, p. 22). The faster brain wave pattern is only partially addressed in CBT-I which focuses on negative sleep talk. However, the emphasis in CBT-I is upon reality testing and/or challenging negative sleep talk, not upon slowing the faster brain wave pattern itself. A behavioral treatment approach which targets the actual here-and-now brain wave frequency

with the goal of slowing the brain wave frequency in the moment at the time when the person wants to go to sleep may further improve their ability to do so.

BRAIN WAVE FREQUENCY AND SLEEP:

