- 1) Lower the threshold for seizures in persons with epilepsy;
- 2) Precipitate mania in bipolar participants;
- 3) Exacerbate parasomnias;
- 4) Prevent adequate ventilation in patients with obstructive sleep apnea; and/or
- 5) Aggravate the day time somnolence to the point where it is no longer safe for the participant to drive, operate machinery and/or make judgments that adequately promote their own and/or the safety and well-being of others.

The risk is generally higher when these illnesses are untreated. Prospective participants treated for any of these illnesses and interested in participating must have the written approval of their treatment provider in order to be eligible. Prospective participants will be screened and informed of these potential risks. If any of these risks (1-5 above) occur during the study, the participant will be asked to immediately discontinue the sleep restriction, and an alternative treatment not involving sleep restriction will be offered. The participant will also have the option of discontinuing the treatment if they prefer this to proceeding with the alternative treatment which does not involve sleep restriction.

SAMPLE SIZE

It is estimated that 320 prospects will need to be screened in order to have 40 per group for a total of 160 participants.

ANALYSIS POPULATIONS

Safety Population: will include all randomized subjects who meet eligibility criteria and meet with their treatment provider for session 1.

Intent-to-Treat Population: will include all subjects who meet with their treatment provider for session 1 and for whom the treatment provider determines the subject meets diagnostic criteria for 780.52 Insomnia Disorder.

Pre-Protocol (PP) Population: will include all subjects who complete the 6 sessions of treatment as well as the 3 month, 6 month and 12 month follow up assessment. It is estimated that 80% of those who complete session 1 will complete session 6. It is estimated that 80% of those who complete session 6 will complete the 3 month, 6 month and 12 month follow up assessments. This will result in 25 participants who will have completed the entire study.

HYPOTHESES

Hypothesis 1: Treatment Effect on Subjective Measures from Weekly Sleep Log

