- 5) Aggravate the day time somnolence to the point where it is no longer safe for the participant to drive, operate machinery and/or make judgments that adequately promote their own and/or the safety and well-being of others.

The risk is generally higher when these illnesses are untreated. Prospective participants treated for any of these illnesses and interested in participating must have the written approval of their treatment provider in order to be eligible. If any of these risks (1-5 above) occur during the study, the participant will be asked to immediately discontinue the sleep restriction, and an alternative treatment not involving sleep restriction will be offered. The participant will also have the option of discontinuing the treatment if they prefer this to proceeding with the alternative treatment which does not involve sleep restriction.

9.0

INVESTIGATIONAL PLAN

9.1

OVERALL STUDY DESIGN AND PLAN: DESCRIPTION

TELEPHONE PRE-SCREENING

- A) Provide information about the study, what to expect and what is required if participating. Use Informed Consent form as an outline and a reference. Ask if the person has any questions.
- B) Assess: Inclusion and Exclusion Criteria
The definition of insomnia will be that of DSM-5.

9.1.1

IN PERSON SCREENING AND DATA GATHERING

Complete diagnostic interview per DSM-5. To be eligible, the person must meet the DSM-5 diagnostic criteria for 780.52 Insomnia Disorder. This includes a cumulative minimum average sum of 30 minutes or more of time spent, adding number of minutes of inability to initiate or return to sleep plus number of minutes of early morning awakening with inability to return to sleep.

If the person does not meet diagnostic criteria, thank them for their interest and inform the person that they are not eligible. Provide the specific reason for ineligibility. For example, the person may not meet one or more required aspect of the diagnostic criteria for Insomnia Disorder per DSM-5.

If the person meets eligibility criteria and DSM-5 diagnostic criteria for insomnia disorder, provide the person with a copy of the Informed Consent form. Have the person follow along as you read the form aloud in their presence.

At the end of this process, if the person is still interested in participating, go through the **Informed Consent Form (ICF) for Participants in Insomnia Study** with the participant.

9.1.2

DSM-5 DIAGNOSTIC SCREENING INTERVIEW

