9.4.10 TREATMENT AFTER DISCONTINUATION

Patients whose sleep symptoms worsen or are determined by the Investigator not to be adequately controlled prior to completing the randomization six week study period will be allowed to discontinue the study and start appropriate treatment at the Investigator's discretion. This new treatment will not be provided by the Sponsor. Patients who initiate a new treatment must be discontinued from the study.

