9.7.2 ANALYSIS POPULATIONS

1. **Safety Population:** will include all randomized subjects who meet eligibility criteria and meet with their treatment provider for session 1.

2. **Intent-to-Treat Population:** will include all subjects who meet with their treatment provider for session 1 and for whom the treatment provider determines the subject meets diagnostic criteria for 780.52 Insomnia Disorder.
3. **Pre-Protocol (PP) Population:** will include all subjects who complete the 6 sessions of treatment as well as the 3 month, 6 month and 12 month follow up assessment. It is estimated that 80% of those who complete session 1 will complete session 6. It is estimated that 80% of those who complete session 6 will complete the 3 month, 6 month and 12 month follow up assessments. This will result in 25 participants who will have completed the entire study.

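### The protocol offers participants harmed by sleep restriction an in-study alternative, yet 9.4.10 read literally removes anyone who starts a new treatment, and follow-up after removal is unclear

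*Protocol*

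**What the plan says.** The Synopsis (Safety Measures) and Section 8.0 (Safety and Tolerability End Points, and again Safety Analysis) list five risks of sleep restriction: seizures, mania, parasomnias, impaired ventilation in sleep apnea, and unsafe daytime somnolence. If one occurs, "the participant will be asked to immediately discontinue the sleep restriction", and "an alternative treatment not involving sleep restriction will be offered". Leaving is a separate choice: "The participant will also have the option of discontinuing the treatment if they prefer this to proceeding with the alternative treatment". The alternative treatment is not named.

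Section 9.4.10 concerns "Patients whose sleep symptoms worsen or are determined by the Investigator not to be adequately controlled" before the six-week period is complete. They may leave the study and start other treatment. The section adds "This new treatment will not be provided by the Sponsor" and then, without qualification, "Patients who initiate a new treatment must be discontinued from the study".

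On follow-up, Section 9.3.3 defines the final assessment of a discontinued patient as the Visit 8 evaluations and sends such patients into a one-week safety follow-up at that visit. Section 9.4.6.3 says that patients who discontinue early should also enter the safety follow-up period. The Schedule of Evaluations in Section 2.0 puts that label over the 3, 6 and 12 month visits. Under Missing Data in Section 8.0, subjects without 12-month follow-up are left out of the 12-month analyses.

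**The concern.** A site facing a participant whose somnolence has become unsafe under sleep restriction has two instructions. One implies that the participant goes on in the study with a different treatment. The other, taken at its word, ends participation once a new treatment starts. Different staff could follow different rules.

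The offer of an alternative depends on the arm. Section 8.0 says that an assignment may or may not involve sleep restriction, and the Introduction describes restriction only as a CBT-I component. The Introduction also names, as a drawback of CBT-I, "increased daytime sleepiness which, for some, is enough to lead them to drop out of treatment". If these participants are removed and not followed, the 12-month comparisons (Hypotheses 8 to 14) lose them mainly from the arms with sleep restriction, and the loss is related to how they fared. If they are kept and switched, the as-randomized contrast is diluted. The two readings push the result in opposite directions.

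**Working it through.** **1. The two rules side by side**

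| | Synopsis and Section 8.0 | Section 9.4.10 |
|---|---|---|
| Trigger | Any of five harms of sleep restriction | Sleep symptoms worse or not adequately controlled |
| Arms | Only those using sleep restriction | All four |
| Treatment | Unnamed alternative, offered to the participant | New treatment, not supplied by the Sponsor |
| Status | Continuing, unless the participant prefers to stop | Discontinued from the study |

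The triggers differ but can overlap. Worsened parasomnia (risk 3) or aggravated daytime somnolence (risk 5) can reasonably be read as worsening sleep symptoms. No cross-reference says which rule then governs.

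**2. Follow-up after discontinuation**

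Under 9.3.3 the last required contact is Visit 8. Under 9.4.6.3 together with the schedule it could be Visit 11. Sections 9.1.3 and 9.4.5 do not settle this: their safety follow-up heading stands over both the end-of-treatment battery, due within a week, and the three later follow-ups. If Visit 8 is the end, the Missing Data rule takes the participant out of every 12-month analysis.

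**3. The plan's own attrition figure**

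Section 9.7.2 expects 80% retention to session 6, then 80% through follow-up, giving 25 completers. 40 × 0.80 × 0.80 = 25.6, so the figure is reproduced per group (over all arms, 160 × 0.64 = 102.4). These rates cover loss from any cause, so losses under the safety rule are already inside them.

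**4. Illustration of direction and scale**

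Inputs from the Introduction: remission 36% with CBT-I and 16.9% in comparison conditions, a difference of 19.1 points. Let s be the share of a sleep-restriction arm affected. The protocol gives no value, so s is assumed between 5% and 33%. The upper end is borrowed from the 0% to 33% dropout the Introduction cites for CBT-I trials with sleep restriction. The comparator stays at 16.9%.

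- Kept and switched, with switchers remitting at 16.9% instead of 36%: difference = (1 − s) × 36 + s × 16.9 − 16.9 = 19.1 × (1 − s).
- Dropped, where the whole arm would have averaged 36% and those dropped would have remitted at 16.9%: difference = (36 − 16.9s)/(1 − s) − 16.9.
- Dropped, where none of them would have remitted: difference = 36/(1 − s) − 16.9.

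| s | Affected among 80 in two arms | Kept and switched | Dropped (16.9%) | Dropped (0%) |
|---|---|---|---|---|
| 5% | 4 | 18.1 | 20.1 | 21.0 |
| 10% | 8 | 17.2 | 21.2 | 23.1 |
| 20% | 16 | 15.3 | 23.9 | 28.1 |
| 33% | 26 | 12.8 | 28.5 | 36.8 |

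Differences are in percentage points. The count of 80 assumes that Combined uses sleep restriction.

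**The case against.** The strongest reply is that the two rules can be read together. Section 9.4.10 is headed as treatment after discontinuation, its trigger is uncontrolled sleep symptoms, and its new treatment comes from outside. Section 8.0 covers specific harms in a continuing participant. This largely stands: the conflict lies in the unqualified last sentence of 9.4.10 and the missing cross-reference, not in the whole section.

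Several stronger readings are tempting, and the documents do not support them.

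- *Only the CBT-I arms can lose participants this way.* Removal under 9.4.10, and the discontinuation reasons in 9.3.3, apply to all arms. Only the switch offer depends on the arm.
- *A switch is a crossover to FOA or Sleep Hygiene.* The alternative is not named. It could be the other CBT-I components without restriction. The session content is in folders outside the protocol, so even restriction in Combined is an inference.
- *Switchers would count as per-protocol CBT-I completers.* Section 9.7.2 says the set "will include all subjects who complete the 6 sessions of treatment", without requiring the assigned treatment. But no efficacy analysis is tied to that set, and classing switchers is commonly left to the SAP. Demanding six sessions of the assigned treatment would itself exclude those who tolerate restriction worst.
- *The expected completers per arm would fall further.* That would count the same losses twice (step 3).
- *The harm would go unrecorded.* Section 9.3.3 puts the discontinuation reason on the eCRF, and 9.5.2.5 requires the actions taken for every adverse event. What is not promised is a report by arm: the safety parameters in 9.7.3 are the C-SSRS.

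The rate may also be low. Of the ten cited trials, seven had dropout of 8% or less, and the mean is (4 × 0 + 7 + 2 × 8 + 11 + 18 + 33)/10 = 8.5%. Dropout from any cause is not the trigger event, the somnolence trigger is demanding, and the exclusions for epilepsy and for sleep apnea above the cutoff narrow the group at risk. The early-termination visit also seeks ISI, SRSM and sleep-log data (9.5.3.8), so post-treatment outcomes are better protected than 12-month ones.

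**Conclusion.** The concern holds as an unresolved conflict with an arm-dependent consequence. The protocol does not say whether the safety alternative is a new treatment under 9.4.10, and it gives two answers on how far a discontinued participant is followed. With the elimination of those lacking 12-month data, removal could selectively drop participants who tolerate sleep restriction poorly.

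The documents do not give the size. The table shows direction and scale only. It rests on an assumed share affected, on remission rates from a cited meta-analysis rather than this trial, and on dropped participants contributing no data. At 10% affected, the illustrative 19.1 points become 17.2 with switchers kept and 21.2 to 23.1 with them dropped. A SAP can decide how switchers are classed, but it cannot recover visits that were never requested. Should-fix, moderate confidence.

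**What to change.** Reconcile the Synopsis and Section 8.0 safety rule with Section 9.4.10, saying whether the safety alternative counts as a new treatment. Reconcile Section 9.3.3 with Section 9.4.6.3 and the schedule on follow-up after discontinuation. Which clinical path applies is for the sponsor.

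Whichever path is chosen, state that:

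- a participant who stops sleep restriction, switches, or is discontinued from treatment is still asked to complete the outcome assessments through Visit 11, unless consent is withdrawn;
- that participant is analysed in the arm randomized;
- stops and switches are reported by arm.

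The per-protocol definition need not change for this. The cost is protocol wording, some extra follow-up effort, and a somewhat diluted as-randomized contrast if switches occur. Most of the recording is already required by 9.3.3 and 9.5.2.5.

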If you participate, your time commitment will include six one hour appointments with your study staff. These appointments will be on a weekday day, at 11:00am, 12:00 noon or 2:00pm. As a participant, you will be assigned to on weekday for a one hour appointment for six consecutive weeks. Please put an X beside each time that works for you on each day.

Monday @ 11:00am; 12:00 noon; 2:00pm

Tuesday @ 11:00am; 12:00 noon; 2:00pm

Wednesday @ 11:00am; 12:00 noon; 2:00pm

Thursday @ 11:00am; 12:00 noon; 2:00p

Treatment providers will be required to declare at least one and preferably two of these times (11am, noon and/or 2pm) as times they will be available to delivery treatment, given two week notice of a participant being assigned. The Research Coordinator will make effort to inform each provider when it is likely they will be assigned a new participant.

The Research Coordinator will inform the treatment provider one week in advance of a probably participant being assigned, also informing the treatment provider of the treatment to be utilized (FOA, CBT-I, Combined and Sleep Hygiene).

The Research Coordinator will keep an Excel spread sheet in order to systematically assign subjects (participants) to treatment. Participants will be randomly assigned to treatment and then assigned to the next treatment provider in a systematic, non-biased manner. The first four treatment providers will be randomly designated by the Research Coordinator as the first, second, third or fourth treatment provider to be assigned the participant. The first participant in the clinical trial will go to the provider declared first to be assigned. The second participant in the clinical trial will go to the provider declared second to be assigned. Similarly for assignment of a participant to the third and fourth provider. The fifth participant will be assigned to the provider who had been randomly designated as the first to be assigned a participant. The assignment will proceed, sixth participant to the provider who had been assigned the second participant in the study, etc. The Research Coordinator will use Excel spread sheet in order to determine which treatment provider is next to be assigned a participant.

At the end of the In Person Screening and Data Gathering, the Research Coordinator will inform the participant of the time and date of their first treatment session and the name of the treatment provider.

The Research Coordinator will direct the participant to arrive a few minutes early and to check in at the front desk in the first floor reception area. The participant will be told to tell the receptionist their name, the name of their treatment provider, and that they are receiving treatment for insomnia in the Insomnia Clinical Research Trial.

The Research Coordinator will schedule the participant with one of the treatment providers. The treatment will be at either 11:00am, 12 noon or 2:00pm depending on which one hour block of time that treatment provider has reserved for treatment delivery. The Research Coordinator will schedule the initial session in Practice Fusion with 5 weekly repeats. The Research Coordinator will then send an email to the treatment provider indicating the name of the client, the time and date on which the first session is scheduled, and the treatment the provider is to deliver (FOA, CBT-I, Combined and Sleep Hygiene).

CLINICAL PROCEDURES

The study staff will follow the six session protocol for treatment delivery. Each of the six sessions is scripted so as to provide standardization, and the study staff will generally be reading the script. The first session is identical across all four treatments. For specifics, see file folders entitled CBT-I, FOA, Combo and Sleep Hygiene.

DATA GATHERING DURING TREATMENT

Ongoing self-report data pertaining to the participant's sleep using a Weekly Sleep Log. Weekly Sleep Logs will be completed by the participant and brought to each treatment session. At the beginning of each session, the study staff will review the Weekly Sleep Log for completion. After the treatment session has ended and during the same day, the study staff will forward the Weekly Sleep Log to the Research Coordinator.

The Research Coordinator will enter the following information onto the DATA SHEET:

1. SL; Sleep Latency (time to fall asleep in minutes)
2. NOA: Number of Awakenings
3. WASO: Wake After Sleep Onset (in minutes)
4. SL + WASO (in minutes)
5. TOB: Total Time Out of Bed in minutes
6. TST: Total Sleep Time (in minutes)
7. TIB: Time In Bed (total, in minutes)
8. SE: Sleep Efficiency = TST/TIB (as a decimal)

9.1.3 SAFETY FOLLOW UP PERIOD

Coordinated and administered by Research Coordinator. Completed after last treatment session; can be on that day but not before the treatment session; must be no later than one week after that date.

FEEDBACK QUESTIONNAIRE:

1. Beck Depression Inventory (BDI)
2. Beck Anxiety Inventory (BAI)
3. Insomnia Severity Index (ISI)
4. Self-Report Sleep Measures (SRSM)
5. Clinical Global Impression (CGI)
6. Clinical Global Impression – Severity scale (CGI-S)
7. Quality of Life Enjoyment and Satisfaction (Q-LES)
8. Columbia Suicide Severity Rating Scale (C-SSRS)

THREE MONTH FOLLOW UP:

WEEKLY SLEEP LOG (WSL)

Data entry completed for one week at each administration [At in person intake, each week during treatment and at 3, 6 and 12 months]

[Each of the following is needed for data entry as an average for the last 7 nights]

1. SL; Sleep Latency (time to fall asleep in minutes)
2. NOA: Number of Awakenings
3. WASO: Wake After Sleep Onset (in minutes)
4. SL + WASO (in minutes)
5. TOB: Total Time Out of Bed in minutes
6. WASO: Waking Time After Sleep Onset in minutes
7. TST: Total Sleep Time (in minutes)

8. **TIB: Time In Bed (total, in minutes)**
9. **SE: Sleep Efficiency = TST/TIB (as a percentage)**
10. **Beck Depression Inventory (BDI)**
11. **Beck Anxiety Inventory (BAI)**
12. **Insomnia Severity Index (ISI)**
13. **Self-Report Sleep Measures (SRSM)**
14. **Clinical Global Impression (CGI)**
15. **Clinical Global Impression – Severity scale (CGI-S)**
16. **Columbia Suicide Severity Rating Scale (C-SSRS)**

SIX MONTH FOLLOW UP:

This is the same as the THREE MONTH FOLLOW UP except that the following three are added.

1. **Beck Depression Inventory (BDI)**
2. **Beck Anxiety Inventory (BAI)**
3. **Insomnia Severity Index (ISI)**
4. **Self-Report Sleep Measures (SRSM)**
5. **Clinical Global Impression (CGI)**
6. **Clinical Global Impression – Severity scale (CGI-S)**
7. **Columbia Suicide Severity Rating Scale (C-SSRS)**

TWELVE MONTH FOLLOW UP:

[figure not shown]
This is the same as the SIX MONTH FOLLOW UP adding the Feedback Questionnaire.

1. **Beck Depression Inventory (BDI)**
2. **Beck Anxiety Inventory (BAI)**
3. **Insomnia Severity Index (ISI)**
4. **Self-Report Sleep Measures (SRSM)**
5. **Clinical Global Impression (CGI)**
6. **Clinical Global Impression – Severity scale (CGI-S)**
7. **Columbia Suicide Severity Rating Scale (C-SSRS)**

A schematic of the study design is presented in [Figure9.1-1](#). The Schedule of Evaluations is presented in Section [2.0](#). Detailed descriptions of each study visit can be found in Section [9.5.6](#).

FIDURE 9.1-1

STUDY DESIGN

9.2

DISCUSSION OF STUDY DESIGN

This is a randomized, open label, sleep hygiene, controlled, 6-week study to compare the efficacy of four (CBT-I, FOA, Combined CBT-I and FOA and Sleep Hygiene) different behavioral approaches for the treatment of adult subjects with insomnia. In this study, investigators will enroll patients, male and female, who are 18 or older to 72 years. Insomnia Severity Index > or = 10 and meet diagnostic criteria for Insomnia Disorder per DSM-5 willing and able to sign Informed consent form not planning on moving away from the area for the subsequent 12 weeks. In this study, safety and efficacy assessments are included during every visit to determine adequacy of response, safety, and tolerability.

9.3

SELECTION OF STUDY POPULATIONS

Inclusion/Exclusion criteria to be assessed at Screening (Visit 1) and Every Visit (Visit 2, 3, 4, 5, 6, 7, 8, 9, 10 and 11)

9.3.1

INCLUSION CRITERIA

All potential participants must meet these inclusion criteria:

1. Both genders
2. Age \geq 18 to 72 years
3. Insomnia Severity Index > or = 10
4. Meet diagnostic criteria for Insomnia Disorder per DSM-5
5. Be willing and able to sign Informed consent form
6. Not planning on moving away from the area for the subsequent 12 weeks.

9.3.2

EXCLUSION CRITERIA

Participants who answer “yes” to any of the following will be excluded:

1. Females who are lactating or who are pregnant
2. Night shift workers, and individuals who nap 3 or more times per week over the preceding month
3. Consumption of caffeine beverages (i.e. tea, coffee, or cola) comprising usually more than 5 cups or glasses per day
4. Participation in another trial for insomnia
5. Persons unable to complete the study questionnaires and psychological tests
6. Persons who are unable to participate for the entire duration of the study, or in the opinion of the investigators, are likely to be non-compliant with the obligations inherent in the trial participation
7. Persons self-describing with severe anxiety or severe depression
 - a. (BDI score of 29 or higher) or severe anxiety (BAI score of 36 or higher).
8. Persons with a history of epilepsy, seizures, or dementia
9. Any significant, severe or unstable, acute or chronically progressive medical or surgical condition
10. Serious head injury or stroke within the past year
11. Current alcohol or substance abuse/dependence (must have >90 days of sobriety)
12. Presence of other neurological disorders (e.g., multiple sclerosis, Parkinson's Disease)
13. Presence of an untreated or unstable medical or psychiatric comorbid condition (e.g., major depressive disorder or psychotic disorder requiring admission within the last two years). People using psychotropic medication, hypnotic or sedative medications may be included if they are on a stable dosage for the last 2 months prior to the study, if the dose remains stable throughout the study, and if the medication is judged to not interfere with the study outcomes.
14. Currently on medications known to produce insomnia (e.g., stimulants)
15. Sleep apnea (AHI >15) or previous diagnosis of. Study participants who use a continuous positive airway pressure (CPAP) device for sleep apnea will be eligible for participation if they are below the apnea/hypopnea cutoff while using CPAP and agree to use the device during study participation.
16. **If the person not eligible** per inclusion and exclusion criteria, thank the person for their interest and inform them that they are not eligible. Also inform the person that regardless, they still have

the option of seeing a health care provider at their own initiative and under whatever financial agreement they may establish with that health care provider (insurance or otherwise).

17. **If the person is eligible** and is interested in being considered, schedule the initial in person screening interview and data gathering.

9.3.3

REMOVAL OF PATIENTS FROM THERAPY OR ASSESSMENT

A premature discontinuation will occur when a patient who signed the ICF ceases participation in the study, regardless of circumstances, before the completion of the study visits and procedures. Patients can be prematurely discontinued from the study after careful consideration for one of the following reasons:

1. Screen failure (failure to meet inclusion/exclusion criteria or pregnancy)
2. Pregnancy
3. Withdrawal of consent
4. Lack of efficacy
5. Protocol violation
6. Noncompliance with treatment plan
7. Lost to follow-up
8. Study terminated by Sponsor
9. Study center terminated by Sponsor
10. Other

